The trial is designed to have adequate power to test the null hypothesis $H_0: \log(\lambda_1 / \lambda_{2/3}) = 0$ versus the alternative hypothesis $H_a: \log(\lambda_1 / \lambda_{2/3}) \geq 1.3$ for the comparison of overall survival between the remaining experimental arm (arm 2) and the standard arm (arm 1). The power analysis is based on the following assumptions: (1) the 2-year overall survival rate of the remaining experimental arm (arm 2) is 57.3% and that of arm A is 48.5%. Under exponential survival distribution, the median survival for the remaining experimental arm is 29.9 months and for the standard arm is 23 months, or a hazard ratio of 1.3 (λ_1 / λ_2) for the standard arm to the remaining experimental arm; (2) an accrual length of 6 years; (3) 303 eligible patients in the standard arm and 303 eligible patients in the remaining experimental arm; (4) additional follow-up of 2.5 years after the last enrollment; (5) a two-sided significance level of 0.05. Under these assumptions, at the time of final analysis, at least 483 deaths are anticipated under alternative hypotheses for the two remaining comparative arms. Without taking into account the expected minimal loss of power due to interim analyses, the power in detecting the survival improvement for the remaining experimental arm (arm 2) as compared to the standard arm is at least 81.9% using a stratified log-rank test.

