With allowance of 20% patient loss due to consent, ineligibility, and specimens of poor quality, we assume that 264 patients on arm A and 264 patients on arm B/C will provide evaluable circulating biomarkers for final analysis. With regards to the first primary objective, we assume the transform of biomarker count difference between post-treatment initiation and baseline follows approximately a normal distribution so that a 2-sample t test would be appropriate. At a 2-sided significance level of 0.05, the study has 90% power to detect a 0.274 standard deviation of cell count difference between the two treatment arms on log scale. With regards to the second primary objective, for the purpose of power analysis, the correlation of the biomarker (baseline or change scores of post-initiation of treatment against baseline) with response rate, 2-year FFS and 2-year OS will be tested for each arm using logistic regression with a single continuous predictor. At a 2-sided significance level of 0.05, the study has at least 90% power to detect a 6% increase of response rate from 80% at the mean of the biomarker to 86% at one standard deviation above of the mean. Similarly, the study has at least 90% power to detect an 11% increase of 2-year FFS from 40% at the mean to 51% at one standard deviation above of the mean, to detect an 11% increase of 2-year OS from 50% at the mean of a biomarker to 61% at one standard deviation above of the mean.

Power Analysis for the Second Correlative Science Substudy (Section 10.1.2):

The primary objective of the second correlative substudy is to evaluate the correlation of several serum markers at baseline or their changes against baseline with response rate (RR), failure free survival (FFS), and overall survival (OS) in small cell lung cancer. They include neuron-specific enolase (NSE), carcinoembryonic antigen (CEA), BB isoenzyme of creatine kinase (CK-BB), angiogenic factors Interleukin 8 (IL-8) and Vascular Endothelial Growth Factor (VEGF), stem cell factor (SCF), granulocyte-macrophage-colony stimulating factor (GM-CSF), and tumor

hypoxia marker osteopontin. The correlation tests are considered exploratory and the Type I errors will not be adjusted for multiple comparisons.

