Most studies of proGRP have reported that approximately 70-80% of patients have increased levels of proGRP in their serum or plasma. The primary endpoint examines the correlation of increases in the plasma proGRP levels with changes in disease status. This strategy is based on the analyses performed for tumor markers used for monitoring and approved by the FDA, such as CA19-9, CA15-3, CA125 and CEA. Changes above a cutoff are compared for to clinical evaluation of stable disease vs. progression. In the secondary studies, the correlation of decreases in proGRP level will be compared to stable disease vs. regression and/or remission designations. The data is analyzed as concordance of 2 X 2 table of clinical outcome vs. a defined change in cutoff levels. For proGRP, 3 levels will be evaluated initially a) the percent increase that is 2.5 times the assay's observed total percent coefficient of variation (CV), b) a percent change that is 2.5 times the assay and biological variation, and c) a change of >25% based on changes used with other cancer biomarkers. The change in disease state is evaluated per sequential pair and per patient. Secondary analyses can determine whether a different cutoff functions better than these 3 cutoffs. Individual patients will be evaluated by following their sequential proGRP values and their clinical status via tables and graphs.

Based on the numbers of patients and samples sufficient for these evaluations for other monitoring biomarkers as submitted to and approved by the FDA, it is recommended that between 150 and 200 patients be enrolled in this study. A sample size of approximately 150 and 200 patients will provide a sufficient number of evaluable patients with 95% confidence and 80% to 90% statistical power for evaluating the association of the change in ProGRP assay values and change in disease status.

For the primary study and the secondary studies of the relationship of proGRP levels at baseline and at each round of chemotherapy and at the end of therapy will be analyzed as defined above.

Analytic Methods

All data from eligible patients with evaluable measures of the biomarker of interest will be included in final analysis. A 2-sided significance level of 0.05 will be used for all tests.

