Descriptive statistics will used to characterize biomarker count or distribution over time and changes against baseline. The change of biomarker count or mean between treatment arms will be tested using a 2-sample t test on a transformed scale such as the use of t test is appropriate. If the normal assumption is violated, Wilcoxon rank sum test, a nonparametric test, will be used. As supplementary analysis, the difference of biomarker count and mean change will be modeled using generalized linear model using appropriate link function.

The correlation of the baseline measure or the change of the biomarker measure relative to baseline with response rate (RR) will be evaluated using logistic regression [86] with and without adjusting for significant confounding variables at baseline. The correlation of the biomarker with failure free survival (FFS) and overall survival (OS) will be evaluated using Cox's proportional hazard model [87] for time to event data without and with adjusting for confounding variables. These analyses will reveal whether the baseline biomarker or its change against baseline during treatment is predictive to RR, FFS, or OS, or whether the correlation is dependent on which treatment is given. In the pooled analysis of all patients on the treatment arms, the interaction between treatment and baseline or change score of the biomarker will be tested to evaluate the predictive value of the biomarker to different treatments.

If a continuous biomarker is significantly correlated with FFS or OS, an optimal threshold for classifying patients into subgroups will be identified by searching the dichotomized level of the continuous predictor at which yields the maximal log rank statistic. Both the raw p-value from the log rank test as well as the adjusted p-value from the maximal log rank statistic [88], which takes the randomness of the maximally selected cutoff point into account, will be provided. Kaplan-Meier curves [89] will be used to describe survival difference for different subgroups of patients classified by predictive biomarker at its optimal cutoff point.

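### The between-arm biomarker test in Section 15.6 leaves out the baseline value as a covariate; ANCOVA would cost nothing and gain from zero to about 9 points of power, depending on quantities the plan does not give

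*Combined protocol and SAP*

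**What the plan says.** Section 15.6 lists as the first primary objective of the first correlative substudy whether the higher-dose arm produces a larger rise in markers of endothelial damage than the 45 Gy arm. Under Analytic Methods the test is: "The change of biomarker count or mean between treatment arms will be tested using a 2-sample t test on a transformed scale". If normality fails: "If the normal assumption is violated, Wilcoxon rank sum test, a nonparametric test, will be used". A generalized linear model of the change is added as supplementary analysis; the text does not list its covariates.

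The power paragraph of the same section works on the change score: "we assume the transform of biomarker count difference between post-treatment initiation and baseline follows approximately a normal distribution". It allows for losing one patient in five and puts the evaluable number as follows: "we assume that 264 patients on arm A and 264 patients on arm B/C will provide evaluable circulating biomarkers for final analysis". The power claim, at two-sided 0.05, reads: "the study has 90% power to detect a 0.274 standard deviation of cell count difference between the two treatment arms on log scale". The analysis text confirms the level: "A 2-sided significance level of 0.05 will be used for all tests". Section 15.3 gives the main-study size as "303 eligible patients in the standard arm and 303 eligible patients in the remaining experimental arm".

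Baseline plasma is drawn before treatment starts (Sections 6.3.1 and 15.6). No biomarker SD and no correlation between baseline and later values appear anywhere.

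**The concern.** A change score subtracts the baseline value with its slope fixed at 1. ANCOVA estimates that slope from the data. In a randomized comparison both target the same between-arm effect, so the choice is about precision. When the true slope is not 1, the change score carries avoidable noise.

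The plan adjusts elsewhere: Section 15.7 pairs the t test with ANCOVA for the quality-of-life change scores, and Section 15.6 fits its biomarker-outcome models with and without baseline confounders. The between-arm biomarker test is the one that names no adjustment. What is at stake is power for one substudy comparison, which already falls a little short of its stated 90%.

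**Working it through.** **Inputs from the documents.** n = 264 per arm, effect d = 0.274 SD of the change on the log scale, two-sided alpha 0.05, stated power 90% (all Section 15.6); 303 eligible per arm (Section 15.3); 20% loss (Section 15.6).

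**Assumed inputs.** rho, the correlation between baseline and follow-up values, and k = SD at follow-up / SD at baseline. Neither is in the documents, so ranges are shown.

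**Step 1: the plan's own figure.** The noncentrality is d × sqrt(n/2) = 0.274 × sqrt(132) = 3.148. By the normal approximation, power = Φ(3.148 − 1.960) = 88.3%; the exact noncentral t gives 88.1%. That is within 2 points of the stated 90%. Conversely, 90% power at 264 per arm corresponds to (1.960 + 1.282) × sqrt(2/264) = 0.282 SD, and 90% power at 0.274 SD needs 281 per arm (exact t).

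**Step 2: the sample size behind it.** 264 is 80% of 330, but 0.80 × 303 = 242. At 242 per arm the t test has 85.3% power.

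**Step 3: variance with baseline as covariate.** Scale the baseline SD to 1.
- Variance of the change score: 1 + k² − 2·rho·k
- Residual variance after adjustment: k²(1 − rho²)
- Ratio R = k²(1 − rho²) / (1 + k² − 2·rho·k)

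The denominator minus the numerator equals (1 − rho·k)², so R never exceeds 1, and R = 1 exactly when the slope rho·k is 1. With k = 1, R = (1 + rho)/2. The effective effect size is 0.274/sqrt(R).

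**Step 4: power with equal variances (k = 1), exact t.**

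| rho | R | 264 per arm | 242 per arm |
|---|---|---|---|
| t test on change | – | 88.1% | 85.3% |
| 0.3 | 0.65 | 97.4% | 96.2% |
| 0.5 | 0.75 | 95.2% | 93.5% |
| 0.7 | 0.85 | 92.6% | 90.4% |
| 0.8 | 0.90 | 91.2% | 88.7% |
| 0.9 | 0.95 | 89.7% | 87.0% |

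A simulation with 4,000 runs per setting at 264 per arm gave 88% for the t test throughout, and 97%, 95% and 91% for ANCOVA at rho 0.3, 0.5 and 0.8.

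**Step 5: power with unequal variances, 264 per arm.**
- rho 0.5, k 1.25: R = 1.5625 × 0.75 / 1.3125 = 0.893; power 91.4%
- rho 0.5, k 1.5: R = 2.25 × 0.75 / 1.75 = 0.964; power 89.3%
- rho 0.5, k 2: R = 4 × 0.75 / 3 = 1; power 88.1%, no gain
- rho 0.8, k 1.25: slope 0.8 × 1.25 = 1; R = 1, no gain

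**The case against.** The strongest reply is that nothing here is wrong. In a randomized comparison the t test on change is unbiased and controls type I error, and the hypothesis concerns a larger rise, which a change score measures directly. All of that stands: this is an efficiency improvement, not an error. It does not defeat the suggestion, because ANCOVA estimates the same between-arm effect from the same samples.

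Four stronger readings are tempting, and the documents do not support them.
- A reader might infer that adjustment lifts power from 88% to 95%. That needs rho of about 0.5 and equal variances, and neither is given. Section 10.1.1 describes a panel of 33 analytes and Section 15.6 several sampling times, so no single rho applies.
- A reader might infer that a change score is inefficient whenever rho is below 1. What matters is the slope, rho × k; at slope 1 the change score loses nothing. Treatment is expected to move these markers, so equal variances cannot be taken for granted.
- A reader might infer that adjustment restores the stated 90%. Even with equal variances it does not at rho 0.9 with 264 per arm, or at rho 0.8 and above with 242.
- A reader might infer that the supplementary model also leaves out baseline. The text names no covariates, so this is unknown.

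It is also fair to say that the consequence is limited: Section 10.1.1 labels these objectives exploratory, and they feed neither the survival endpoint nor a stopping rule.

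**Conclusion.** The point holds as a minor, costless improvement. The named between-arm test ignores a baseline value that is already in hand. At 264 per arm and 0.274 SD of change, adjusting for it would raise power by about 9 points at rho 0.3, 7 at 0.5, 4.5 at 0.7 and 1.5 at 0.9 under equal variances. The gain shrinks to none as the slope of follow-up on baseline approaches 1. The downside is one degree of freedom, which is negligible at this size.

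Separately, the 90% power statement should be corrected to about 88% at 264 per arm. The 264 itself does not follow from a 20% loss on 303 per arm. The true number may be lower than 242, because Section 5.6 excludes patients registered after one cycle of chemotherapy from the companion studies; the documents do not say how many that is.

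**What to change.** In Section 15.6, Analytic Methods, make the between-arm test an ANCOVA of the log-transformed follow-up value (or of the change; the arm effect is identical) on arm and log-transformed baseline. Name the sampling time used for the planned comparison, since several are listed. Use a rank-based ANCOVA if normality fails, and keep the change-score t test as a sensitivity analysis. State which covariates the supplementary generalized linear model contains.

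In the power paragraph for the first substudy, either give about 88% for 0.274 SD at 264 per arm or change the detectable difference to 0.282 SD for 90%. Reconcile 264 with 80% of 303 (242 per arm, about 85% for the t test). If power is quoted for ANCOVA, state the assumed rho and SD ratio and show a range.

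The cost is a few sentences of plan wording, with no new samples and no change to the main trial. It should be settled before the biomarker data are analysed, so that the covariate is not chosen after seeing results.

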Plasma will be used for the assay. We will use the multiplexed bead suspension arrays for 33 C/AFs (Biosource™ Human Cytokine 30-Plex for Luminex™ panel, Biosource, Camarillo, CA; Lincoplex™ Human Cardiovascular Disease I kit, LINCO Research/Millipore, St. Charles, MO). The Luminex Multiplex Cytometric Bead Array (Multiplex) assay is ideal for exploratory investigations using statistical support. The assay has many advantages. It requires as little as 50 µl of plasma, rather than the 100-200 µl that is required for the routine ELISA procedures. In addition, the Multiplex has an advantage over the ELISA in its ability to measure up to 25-33 cytokines in one run using a single sample, thereby providing relative concentrations among 25-33 cytokines and also minimizing the variance of the data.

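### Biomarker cut-offs are chosen by the maximal log-rank statistic and displayed on the same patients; the planned adjusted p-value does not correct the displayed separation

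*Combined protocol and SAP*

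**What the plan says.** The rule is in Section 15.6, Analytic Methods. A cut-off is sought only after an entry condition, that the continuous marker is significantly related to failure-free survival (FFS) or overall survival (OS). For such a marker, "an optimal threshold for classifying patients into subgroups will be identified by searching the dichotomized level of the continuous predictor". The criterion is the level "at which yields the maximal log rank statistic". At that level the plan reports "Both the raw p-value from the log rank test as well as the adjusted p-value from the maximal log rank statistic", and explains that the adjusted value allows for the cut having been selected. Kaplan-Meier curves "will be used to describe survival difference for different subgroups of patients classified by predictive biomarker at its optimal cutoff point".

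The same subsection sets the level: "A 2-sided significance level of 0.05 will be used for all tests". It also plans Cox models for each marker against FFS and OS, with and without adjustment.

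Section 15.6 does not state a hold-out sample, cross-validation or any other correction of the displayed effect. It does not state the range of cuts to be searched, or whether the search is per arm or pooled. The panel in Section 10.1.1 is large: "We will use the multiplexed bead suspension arrays for 33 C/AFs".

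**The concern.** A cut chosen because it separates the survival curves best will, on those same patients, separate them better than it would on new ones. Two selections act here. Only markers that look prognostic in this sample are searched, and then the most favourable cut is kept. The adjusted p-value answers whether the best cut is more extreme than a search would produce by chance. It does not shrink the curves, which are how the plan says the subgroup difference will be described. It also takes no account of the first selection.

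At stake is how the correlative results are read: a threshold and a pair of curves that look informative for a marker with no effect, and that exaggerate the separation for a marker with a modest one. The trial's primary survival comparison is not affected.

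**Working it through.** **Inputs from the documents.** Evaluable patients: 264 per arm in the first substudy and 230 per arm in the second (Section 15.6), so 528 and 460 pooled. Two-year OS 50% and FFS 40% at the marker mean (Section 15.6). Accrual 6 years and 2.5 years of further follow-up (Section 15.3), so censoring between 30 and 102 months. Entry test at two-sided 0.05.

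**Assumptions.** Normally distributed marker with no effect; exponential survival; uniform censoring; cuts searched over the central 80% or 60% of marker values.

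**The plan's own figure.** None is given for the cut-off step. The nearest is power of at least 90% with 230 patients for two-year OS of 50% at the mean against 62% at one SD above. With b = ln(0.62/0.38) = 0.490, power = Φ(√(230 × 0.5 × 0.5 × 0.490²) − 1.96) = Φ(3.71 − 1.96) ≈ 0.96. The statement holds, so the sample-size inputs are usable.

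**Simulation.** Each data set was kept if the continuous Cox score test gave p < 0.05. The log-rank Z(c) was then computed at every cut c in the range, c* was the cut with the largest |Z(c)|, and the Cox hazard ratio at c* was recorded, expressed above 1. There were 10,000 to 20,000 data sets per setting, of which about 500 to 1,050 passed the entry test.

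Median hazard ratio at c* when the truth is 1.0:

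| Analysis | n | Central 80% | Central 60% |
|---|---|---|---|
| Per arm | 230 | 1.65–1.67 | 1.58–1.59 |
| Per arm | 264 | 1.59–1.61 | 1.53 |
| Pooled | 460 | 1.41–1.44 | 1.39 |
| Pooled | 528 | 1.38–1.40 | 1.35 |

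At n = 230 the median runs from 1.53 (central 50%) to 1.73 (central 90%).

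**Check by hand.** With the central 80% searched, the median raw p is about 0.0027, so |Z| ≈ 3.0. The hazard ratio is roughly exp(Z/√(d·q(1−q))) for d deaths and a fraction q in one group.
- n = 264, d = 217: q = 0.5 gives exp(3.0/7.37) = 1.50; q = 0.2 gives exp(3.0/5.89) = 1.66.
- n = 528, d = 434: the same splits give 1.33 and 1.43.

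The simulated medians lie inside these brackets.

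**What the curves would look like.** As an illustration, take two-year survival of 50% with the hazards placed symmetrically about the average. A ratio of 1.6 gives 0.5^(1/√1.6) = 58% against 0.5^(√1.6) = 42%. A ratio of 1.4 gives 56% against 44%.

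**P-values for null markers.**
- Without the entry test, central 80%: raw p < 0.05 in 43 to 45%, adjusted p < 0.05 in about 4%. The adjustment does its job for the search.
- After the entry test: raw p < 0.05 in 96 to 100%, adjusted p < 0.05 in about 43 to 52%. The adjustment was not built for the entry selection.

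**How much is the cut and how much the entry test.** A separate run at n = 264 gave a hazard ratio of 1.64 for null markers passing the entry test (the run above has mean 1.65, median 1.61), and 1.30 with ten-fold cross-validated groups. On the log scale, ln 1.30 / ln 1.64 = 0.262/0.495 = 53%, so about half of the excess comes from the entry test. In that run, real effects of 1.15 and 1.25 per SD were shown as 1.73 and 1.84, against true values at the chosen cut of 1.27 and 1.46. Cross-validation gave 1.33 and 1.46.

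**Sensitivity to n.** 264/0.80 = 330 and 230/0.70 = 329, whereas the current target is 303 per arm. Using 303, the evaluable numbers are 242 and 212, and the medians become 1.65 and 1.70 per arm, 1.43 and 1.45 pooled (central 80%).

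**The case against.** Several points on the other side stand.

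- A reader might infer that the plan rests on an uncorrected p-value. It does not: the sentence that provides the raw value also provides the adjusted one and says why. The general 0.05 statement does not make the raw value the basis for inference at the cut.
- A reader might take 1.6 as the size of the problem. That figure is per arm. The by-arm wording in Section 15.6 belongs to the power calculations, a pooled analysis is also planned, and the cut-off paragraph does not say which applies. Pooled, the figure is about 1.4.
- A reader might count 33 analytes × 2 endpoints × 2 arms × 0.05 = 6.6 false entries. That counts tests under per-arm analysis, not markers. FFS and OS share deaths, so fewer distinct markers would enter, and pooled testing gives 33 × 2 × 0.05 = 3.3.
- A reader might conclude that multiplicity control has been overlooked. Section 15.6 declares the second substudy's correlation tests exploratory and unadjusted, and Section 10.1.1 calls the first substudy's objectives exploratory, although Section 15.6 lists them as primary for that substudy. This is an open choice.
- The curves are not the only effect reported. Cox models for the marker are already planned, and no hazard ratio at the cut is promised; the ratio is used here only to measure the separation the curves would show.
- ProGRP is grouped at a fixed 50 pg/mL, so that analysis is outside the problem.

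None of this corrects the curves. Exploratory status can justify an unadjusted entry test; it does not make a display at a searched cut unbiased.

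**Conclusion.** The concern holds in a limited form. Followed as written, the rule displays a separation that is too large on average, because the cut is chosen and shown on the same patients with no correction stated. For a null marker that passes the entry test, the median hazard ratio shown is about 1.5 to 1.7 per arm and about 1.35 to 1.45 pooled, against 1.0. These figures rest on the assumed search range and survival model. They are conditional on passing the entry test, which about 5% of null tests do. Part of the excess comes from that test rather than from the cut.

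The adjusted p-value is a real safeguard for the search, but not for the entry selection or the size of the displayed effect. The documents do not support reading this as a threat to the primary analysis. Nor do they say that the thresholds will be used to plan a later trial or guide care.

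**What to change.** In Section 15.6, Analytic Methods:

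1. Draw the Kaplan-Meier curves, and any hazard ratio at the cut, from cross-validated group assignment (cut chosen in the training folds and applied to the held-out fold), or at a cut fixed in advance such as the median.
2. Base inference at the selected cut on the adjusted p-value only, and do not present the raw value as a test.
3. Present the already planned continuous Cox hazard ratio, per SD, as the main effect.
4. State whether the search is per arm or pooled, and over what range of marker values.
5. Label the thresholds hypothesis-generating, because the entry test is unadjusted and neither cross-validation nor a fixed cut removes that selection.

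A false-discovery-rate limit on entry would address the remaining part, but it is optional given the declared exploratory status.

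The cost is SAP wording and a little more programming, with no new patients or samples. The displayed separations will be smaller.
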